Due to the high cost of sugammadex, some researchers have hypothesized that a lower dose is required when combined with neostigmine. A 2015 study from Beirut in adults undergoing elective surgery demonstrated that a dose of 2 mg/kg of sugammadex combined with neostigmine 0.05 mg/kg was non-inferior to the standard dose of 4 mg/kg of sugammadex in reversing deep NMB, defined as returning from a TOF count of 0 to a TOF ratio of 0.9 within 5 minutes, with similar times to extubation as well as no cases of recurarization in the post anesthetic care unit (PACU) (16). Lobaz, Sammut and Damodaran reported in 2013 the use of sugammadex as rescue therapy for a 71-year-old patient with end stage renal disease who was unable to be weaned off the ventilator almost five hours after receiving a single 1.2 mg/kg dose of rocuronium. He had initially achieved a TOF of 4, was reversed with 2.5 mg of neostigmine 45 minutes after induction, but failed to maintain adequate spontaneous ventilation despite his TOF remaining at 4, and was transferred to the intensive care unit 3 hours post induction. There, his TOF steadily declined to 2, as a result of which he received a 6 mg/kg dose of sugammadex, causing him to be successfully extubated ten minutes later (17). It is similarly important to dose sugammadex appropriately; Carollo et al. published a case report in 2019 of an 8-month-old patient who had recurarization after a 4 mg/kg dose of sugammadex was given with a TOF count of 2/4, which fortunately resolved after a second 4 mg/kg dose of sugammadex (18).

Lastly, known common adverse effects of neostigmine include bradycardia, nausea and vomiting (19), while the use of sugammadex has been found to lead to nausea, vomiting, hypotension and headache in \geq 10% of patients (5). There have also been case reports of marked bradycardia possibly leading to cardiac arrest with the use of both agents.

Page 6 of 30 Version: 3 (10/14/2024)

4. Study Endpoints

Primary study outcome:

The time taken to achieve a TOF ratio of 0.9 after the use of the intervention drug versus placebo in a patient population that has already received neostigmine for NMB reversal.

Secondary study outcome:

The percentage of patients who achieve a TOF ratio of 0.9 within 1 minute, 2 minutes, 5 minutes, and 10 minutes.

Safety outcomes:

The incidence in PACU (measured in %) of:

- i. Nausea,
- ii. Vomiting,
- iii. Bradycardia²,
- iv. Tachycardia³, and
- v. Hypotension⁴.

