These patients will be randomized using the Emory University REDCap (Research Electronic Data Capture) software to six groups: 2 mg/kg (the lowest dose approved by the FDA), 1 mg/kg, 0.5 mg/kg, 0.25 mg/kg, 0.125 mg/kg of sugammadex and placebo. Doses would be based on actual body weight. The time taken to reach a TOF ratio of 0.9 thereafter would be measured. If the patient fails to achieve this goal by 10 minutes, sugammadex would be given in 2 mg/kg increments until the patient reaches this threshold and can be safely extubated. The TOF ratio would be measured again at 30 minutes after arrival at the PACU to exclude delayed residual NMB with the plan to give further 2 mg/kg doses of sugammadex if detected.

The inclusion of a placebo group would allow us to examine if patients may recover spontaneously over that time without needing any sugammadex at all, and what parameters may predict that subset of patients. It will also improve the dose response modelling, in that randomization has been weighted so that patients who are least likely to need sugammadex (i.e. if they achieved a TOF count of 4 twitches without fade) are more likely to be in the placebo group or at the lowest dose of sugammadex that is being tested.

The time taken to a TOF ratio of 0.9 after the intervention drug has been given would be compared for statistically significant differences, controlling for the:

- TOF count (3 twitches, 4 twitches with fade, 4 twitches without fade), and
- TOF ratio (0 to < 0.9)

15 minutes after neostigmine has been given and prior to giving the intervention drug.

Quantitative neuromuscular monitoring will be carried out using electromyography, which measures the TOF ratio every 20 seconds. The TOF count (between 0 to 4) and the TOF ratio (0 to 1) would be measured and recorded at baseline and after administration of the study drug. If the TOF ratio remains < 0.9 after this, or if the patient exhibits any symptoms or signs of residual NMB blockade, a further 2 mg/kg dose of sugammadex would be given until the patient achieves a TOF ratio of 0.9.

Page 8 of 30 Version: 3 (10/14/2024)

7. Statistical Analysis Plan

Power Analysis

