An *a priori* power analysis was conducted using G*Power 3.1.9.4 (20). We used an ANOVA F-Test for one-way omnibus difference between groups, alpha threshold of 0.05 for rejecting the null hypothesis, statistical power of 0.80 and a "very large" effect size of 0.765 was calculated based on results from a 2013 randomized controlled trial that examined time from TOF count = 4 to TOF ratio 1.0 comparing neostigmine to three different doses of sugammadex: 0.5, 1.0, and 2.0 mg/kg (15). This gave a required sample size of N=24. This number was increased to N=36 to account for patients with poor modeling from a high starting TOFR (resulting in few data points for that patient) or incomplete recovery within the maximum ten minutes allotted. An anticipated 70% of those enrolled will become ineligible because of an initial TOFR of 90% or greater, thus not requiring any medications, so up to 120 patients may need to be recruited and screened, but only 36 will receive any treatment.

Methodology

Randomization will occur with permuted block randomization, divided into 18 groups, to ensure proportional allocation of participants in each group over time. Dose randomization will be assigned after stratifying by initial TOFC, with a set number of patients recruited for each group, as seen the table below. This ensures that patients who likely need a lower dose are more likely to receive it. Randomization will not occur until participation is assured, i.e., their TOFR is <0.90.

Table 1: Randomization plan for patients (n=36)

| Sugammadex Dose (mg/kg) → | | 0.00 | 0.125 | 0.25 | 0.50 | 1.00 | 2.00 | | | |
|---------------------------|-----------------|------|--|----------|------------|---------|---------|------|-------|----|
| Initial TOFR | Initial TOFC | Fade | placebo | | | | | | Total | |
| ≥ 0.9 | NA | NA | No treatment; track for adverse events | | | 0 | | | | |
| | | 4 | No | 3 pt | 3 pt | 2 pt | 2 pt | 1 pt | 1 pt | 12 |
| < 0.9 | 4 | Yes | 2 pt | 2 pt | 2 pt | 2 pt | 2 pt | 2 pt | 12 | |
| | 3 | NA | 1 pt | 1 pt | 2 pt | 2 pt | 3 pt | 3 pt | 12 | |
| < 0.9 | 0-2 | NA | No t | treatmen | t; track f | or adve | se even | ts | 0 | |
| Total # of Patients (pt) | | | 6 | 6 | 6 | 6 | 6 | 6 | 36 | |

Statistical Methodology

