Assuming assumptions are valid, an increasing exponential regression model with random intercept will be fitted with Time of Four Ratio versus Time, stratified by the natural log of the five dose levels (modeled below). This translates to a slow response initially followed by a more rapid response later. The random intercept will allow for different initial TOFR values.

Page 9 of 30 Version: 3 (10/14/2024)

$$TOFR = \frac{1}{B}e^{(A+time)/B} + TOFR_{initial} + C * \ln(dose)$$

"Success" will be defined as TOFR of ≥0.9 within 5 minutes for 95% of patients, following the model estimate, adjusting for the 95% confidence intervals of the estimates, based on initial TOF ratios, which may be grouped as needed. A secondary analysis will be conducted by TOFC to determine optimal dose at each TOFC level, and if TOFC correlates strongly with TOFR.

8. Data and/or Specimen Banking

N/A

9. Sharing of Results with Participants

N/A

10. Study Timelines

All subjects are anticipated to participate in the study from the start of their surgery to the time of their discharge from the PACU, which should be on the same day. It is expected that 1 year would be required to enroll all study subjects, and for the study to be completed by July 2023.

11. Inclusion and Exclusion Criteria

Individuals will be screened for eligibility at the anesthesia pre-admission clinic.

Inclusion criteria:

- Patients aged 18 years and above who will
- Undergo an elective surgery in the main operating room or outpatient surgery center at Grady Memorial Hospital,
- Receive general anesthesia (standardized to sevoflurane for maintenance),
- Receive rocuronium for NMB,
- Receive neostigmine for NMB reversal,
- Achieve a TOF count of at least 3 twitches but not a TOF ratio of 0.9 fifteen minutes after neostigmine has been given, and
- Able and willing to provide informed consent.

Exclusion criteria:

Page 10 of 30 Version: 3 (10/14/2024)

- Pregnancy and/or lactating,
- BMI ≥ 40,
- Severe renal impairment, i.e. chronic kidney disease stages IV and V as defined by GFR < 30 ml/min/1.73 m² (21),
- Severe hepatic impairment, i.e. Child-Pugh score C⁵ (22, 23),
- Pre-existing neuromuscular disease,
- Anticipated need for postoperative intubation, and/or
- Known hypersensitivity reactions to rocuronium, neostigmine and/or sugammadex.

12. Population

We will not be including the following special populations:

- Adults unable to consent
- Individuals under the age of 18 years
- Pregnant women

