- Did not require general anesthesia for surgery,
- Did not require NMB,
- Did not receive neostigmine for NMB reversal,
- Had a TOF count < 3 or a TOF ratio ≥ 0.9 fifteen minutes after neostigmine, or
- Remained intubated in the immediate postoperative period.

As the study intervention is a one-time dose of the study drug in the OR, no further action should be required if the patient decides to later withdraw from the study. The study will be terminated when the number of participants has reached the required threshold.

17. Risk to Participants

The most common risks of sugammadex as listed by the FDA (5) include:

- Nausea (23-26%)
- Vomiting (11-15%)
- Pain (36-52%)

Uncommon but serious risks of sugammadex include:

- Hypotension (4-13%)
- Tachycardia (2-5%)

Page 12 of 30 Version: 3 (10/14/2024)

- Bradycardia (1-5%)
- Anaphylaxis (0.3%)

Notably, all of these are known to be risks of general anesthesia as well as surgery and are routinely monitored for and treated in the PACU.

18. Potential Benefits to Participants

All study subjects will have any residual NMB reversed, which will prevent any postoperative complications such as respiratory compromise or weakness.

19. Compensation to Participants

N/A

20. Data Management and Confidentiality

Data to be collected include:

- Baseline demographics: MRN, date of birth, sex (male/female), race (white, black, American Indian or Alaska Native, Asian, Native Hawaiian or Other Pacific Islander, two or more races), ethnicity (Hispanic or Latino, not Hispanic or Latino), weight (kg)
- ii. Preoperative details: ASA status (I-IV)
- iii. Surgery details: date of surgery, diagnosis, surgery, start case time (hr: min), end case time (hr: min)
- iv. Anesthesia details: if succinylcholine was used (Y/N), total amount of rocuronium given (mg), the last dose of rocuronium that was given (mg), the time that the last dose of rocuronium was given (hr:min), neostigmine dose (mg), the time that neostigmine was given (hr: min), the time that the study drug was given (hr: min).
- v. TOF ratio (0-1)
 - Before any paralytic is given at the start of the case
 - Before neostigmine is given at the end of the case
 - Before the study drug is given
 - 30 minutes after PACU arrival
- vi. TOF count (0-4 ± fade)
 - Before neostigmine is given at the end of the case
 - Before the study drug is given
- vii. The time taken to achieve a TOF ratio of 0.9 (seconds).

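### The unparalysed TOF ratio is recorded but never used, so a patient whose own unblocked reading is below 0.9 can be randomised as inadequately reversed

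*Combined protocol and SAP*

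**What the plan says.** The data list in Section 20 includes four TOF ratios per patient. The first is taken "Before any paralytic is given at the start of the case", so the plan holds each patient's own unblocked value on the monitor. No threshold is attached to it, and it does not appear in any later rule.

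The rules that decide who enters and what counts as recovery use other readings:

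- **Inclusion (Section 11):** "Achieve a TOF count of at least 3 twitches but not a TOF ratio of 0.9 fifteen minutes after neostigmine has been given".
- **Randomisation (Section 7, Methodology):** "Randomization will not occur until participation is assured, i.e., their TOFR is <0.90".
- **Withdrawal (Section 16):** "Had a TOF count < 3 or a TOF ratio ≥ 0.9 fifteen minutes after neostigmine".
- **Primary outcome (Section 4):** "The time taken to achieve a TOF ratio of 0.9 after the use of the intervention drug versus placebo".
- **Success (Section 7, Statistical Methodology):** a ratio of 0.9 or more within 5 minutes for 95% of patients, read from the fitted model.
- **Adjustment (Section 6):** TOF count and TOF ratio after neostigmine and before the study drug.
- **Rescue (Section 6):** if 0.9 is not reached by 10 minutes, "sugammadex would be given in 2 mg/kg increments until the patient reaches this threshold and can be safely extubated". A second sentence in the same section repeats the 0.9 target.

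**The concern.** A fixed cut of 0.9 is a sound marker of recovery only if the patient reads at least 0.9 on that monitor when there is no block at all. The plan collects the value that would show this and then leaves it aside.

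Take a constructed case. The unparalysed reading is 0.87. Fifteen minutes after neostigmine the reading is 0.86, with four twitches and no fade. Every written entry rule admits this patient, although block has essentially gone. If the low reading persists, time to 0.9 then reflects the monitor set-up and not the dose.

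Three things would follow. A place among 36 goes to a patient without the condition under study. The dose-response fit receives a flat curve that starts close to the target. And the rescue text, whose only written end is a ratio of 0.9 together with safe extubation, does not say what happens to a patient whose recorded unblocked value lies below 0.9.

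**Working it through.** **1. Is the reading used anywhere?** The places listed above were compared. Inclusion, randomisation, withdrawal and the adjustment covariates use post-neostigmine values. The primary outcome, success and rescue use an absolute 0.9, with no scaling to the patient's own value. Section 6 also says the ratio is recorded at baseline, but it neither defines baseline nor attaches a rule to it.

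**2. Does another provision close the gap?** Two come near.

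- Section 11 excludes "Pre-existing neuromuscular disease". That removes known disease, not a low reading from another cause.
- Section 7 raises the sample from 24 to 36, partly for patients with a high starting ratio or incomplete recovery in ten minutes. That allows for lost information but does not separate residual block from a low unblocked reading.

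**3. What does 0.9 mean for such a patient?** As a fraction of the patient's own value b, the target is 0.9 / b.

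- b = 0.80: 0.9 / 0.80 = 113%
- b = 0.85: 0.9 / 0.85 = 106%
- b = 0.89: 0.9 / 0.89 = 101%

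In each case the target exceeds full recovery to the starting value.

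**4. Where would such patients be allocated?** Section 3 links detectable fade at four twitches to ratios of about 0.1 to 0.4, so a reading in the 0.8s would probably be classed as no fade. The plan does not define how fade is scored, so this is conditional. Table 1 gives the no-fade stratum 3, 3, 2, 2, 1 and 1 patients from placebo up to 2 mg/kg. Placebo plus 0.125 mg/kg therefore receives 3 + 3 = 6 of 12 (50%), against 6 + 6 = 12 of 36 (33%) overall. Non-reachers from this stratum would fall more often on the lowest doses. Adjusting for TOF count would absorb part of that. Adjusting for initial ratio would not explain a patient who starts near 0.9 and stays flat.

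**5. How likely is at least one?** The documents give no frequency. With an assumed rate q among those randomised, the chance is 1 − (1 − q)^36.

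| Assumed q | Chance of at least one in 36 |
|---|---|
| 0% | 0% |
| 0.1% | 1 − 0.999^36 = 3.5% |
| 1% | 1 − 0.99^36 = 30% |
| 3% | 1 − 0.97^36 = 67% |
| 5% | 1 − 0.95^36 = 84% |

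**6. Could the entry rule concentrate them?** The plan's screening figure reproduces: 36 / (1 − 0.70) = 120. The 70% who leave do so because they read 0.9 or more, while a patient with a low unblocked reading tends to stay. If 1% of those recruited were affected, and all stayed below 0.9 with at least three twitches, their share among those randomised would be 0.01 / 0.30 = 3.3%. The chance of at least one would be 1 − (1 − 0.0333)^36 = 70%. This adds two assumptions to an unknown rate.

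**7. Is omnibus power threatened?** Not much. With the plan's effect size of 0.765, alpha 0.05 and six groups, the one-way F test has power 0.92 at 36 patients. Losing 10% (32 left) gives 0.87, and losing 20% (29 left) gives 0.82. The exposure is in the recovery times and the modelled success estimate.

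**The case against.** The strongest reply is that the premise lies outside the documents. Nothing in them says that an unparalysed patient reads below 0.9 on this electromyographic monitor, or how often. The chosen rates therefore decide the size of the answer, and at zero the problem vanishes. That stands, and it is why the table runs from 0% and is only illustrative.

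A reader might infer three stronger claims. None is supported.

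- **That such a patient cannot reach 0.9.** This assumes the low reading lasts through the case. A fault in the set-up at the start may correct itself or be corrected, and one early reading does not fix a ceiling.
- **That one such patient takes 17 percentage points (1 of 6) off an arm judged against 95%.** Success is taken from a model fitted across doses, with allowance for confidence intervals and initial ratio. No arm of six is judged by its raw proportion. The plan also does not say how a patient who never reaches 0.9 enters the time outcome, so counting that patient as a failure of the dose would itself be an inference.
- **That the rescue passages contradict each other.** They agree on 0.9. What is missing is any statement for a patient whose unblocked value is lower, which is a gap for one kind of patient.

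It is also fair to say that the increase to 36 gives some slack for uninformative patients, and that an entry cut at 0.9 is incomplete. A patient with an unblocked value of 0.91 would still need 0.9 / 0.91 = 99% of it.

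What survives is the textual point. A value that could identify these patients before randomisation is collected and not used.

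**Conclusion.** The concern holds as a minor, inexpensive improvement. The pre-paralytic ratio plays no part in entry, randomisation, endpoint, adjustment, success or rescue, and no other provision distinguishes a low unblocked reading from residual block.

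The consequence is conditional. It needs at least one patient with an unblocked reading below 0.9, and that reading must persist to the post-neostigmine measurements. Loading on the lowest doses further requires that such patients be classed as no fade. Under these conditions a patient may miss 0.9 for reasons unrelated to dose. The probability is unknown: from 0% to 84% for at least one in 36 over the assumed range of 0% to 5%. Omnibus power is little affected.

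**What to change.** Add to Section 11, with a matching line in Section 16: *The TOF ratio on the study monitor before any paralytic is at least 0.9. If it is lower, the set-up is checked and the reading repeated before rocuronium. Patients still below 0.9 are screen failures and are not randomised.* The value is already on the data list and precedes randomisation, so the criterion creates no post-randomisation exclusion.

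For patients already randomised, specify a sensitivity analysis that either excludes those with a pre-paralytic ratio below 0.9 or normalises the ratio to the pre-paralytic value. Normalising also covers values just above 0.9. It needs the serial readings described in Section 6 to be kept; the Section 20 list does not name them.

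The sponsor should reconcile the Section 6 rescue passages with a patient whose recorded unblocked reading is below 0.9. No clinical rule is proposed here.

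The cost is a few extra screen failures. If 1% of recruited patients were affected and would otherwise all have been randomised, recruitment would rise from 36 / 0.30 = 120 to 36 / 0.29, about 125. At 5% it would be 36 / 0.25 = 144, above the 120 stated in Section 14. Both rates are assumptions.

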For the safety outcomes, patients who were recruited but did not receive the intervention drug will be compared to patients who did receive the intervention drug to determine if their rates of adverse effects are similar. However, the sample size in this study is too low to perform formal non-inferiority tests on this data.

5. Study Intervention/Investigational Agent

Study intervention:

Patients will be randomized to six groups: 2 mg/kg (the lowest dose approved by the FDA), 1 mg/kg, 0.5 mg/kg, 0.25 mg/kg, 0.125 mg/kg of sugammadex and placebo (normal saline).

The Grady Memorial Hospital operating room pharmacy will store and dispense the study drug, while the anesthesia provider in the operating room will administer it.

As elaborated before, sugammadex is a FDA-approved drug that is in routine clinical use for NMB reversal.

Page 7 of 30 Version: 3 (10/14/2024)

² Heart rate < 60 beats per minute over two or more recordings if not present pre-operatively

³ Heart rate > 100 beats per minute over two or more recordings if not present pre-operatively

⁴ Systolic blood pressure < 90 mmHg and/or mean arterial pressure < 65 mmHg over two or more recordings

The study protocol was submitted to the U.S. FDA, and found to be exempt from IND regulations (PIND 162798 dated 2022-Jul-13).

6. Procedures Involved

This project is a double-blind randomized placebo-controlled dose-response trial that aims to determine the time taken to achieve adequate reversal comparing five doses of sugammadex as rescue therapy following inadequate reversal with neostigmine.

We will identify patients in the Grady Memorial Hospital OR who are scheduled to undergo an elective surgery under general anesthesia, received rocuronium for NMB and neostigmine for NMB reversal, and achieved a TOF count of at least 3 twitches but not a TOF ratio of 0.9 fifteen minutes after neostigmine has been given.

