- viii. Postoperative details: if there was any of the following adverse effects: nausea, vomiting, bradycardia, tachycardia, hypotension (Y/N).

Page 13 of 30 Version: 3 (10/14/2024)

Baseline demographics and postoperative complications will be collected for patients who were enrolled but did not meet the study inclusion criteria to receive the intervention drug and their data will be used as a control group for the safety outcomes.

The data collection form is in the Emory University REDCap database but a similar form has been attached to this protocol as an Excel spreadsheet. Data would be collected by the study team in the OR and PACU. Data will be stored on the Emory University REDCap and OneDrive databases and may also be sent confidentially between study team members through the Emory University Outlook email network. The REDCap and OneDrive databases as well as the Outlook email network are all secure, encrypted and password protected. Paper consent forms will be stored in a locked box in the principal investigator's office at Grady Memorial Hospital. All data and records will be retained for at least 6 years following study completion.

Results will be reported in an aggregate form and in a de-identified manner. The form with protected health information (date of birth, date of surgery and MRN) will be recorded on a form separate to the form with data to be analyzed. Only study team members will have access to the form that links the study IDs with protected health information. [name], the biostatistician for the Emory University Department of Anesthesiology, will conduct the data analysis in collaboration with the principal investigator.

If a participant declines to participate in all portions of the study, the participant will not be assigned a study ID number and the study team members will refrain from collecting any data on the participant. If the participant agrees to participate in some portions of the study but not others, the participant will be assigned a study ID number and the study team members will be instructed to collect data only on those aspects of the study to which the participant has agreed to participate. These procedures will help prevent unauthorized inclusion of the patient's data in the database.

21. Plans to Monitor the Data to Ensure Safety of Participants and Data Integrity

X More than minimal risk

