Review our Data and Safety Monitoring Questionnaire and insert the relevant monitoring table at the end of this section. Also upload the completed questionnaire in the "Basic Study Information" smartform section in eIRB, question #8, as a separate document.

| S | Select one of the following: | | |
|---|------------------------------|--|--|
| | ☐ Medium Complexity | | |
| | ☐ High Complexity Category A | | |

The study team will review the safety endpoints (nausea, vomiting, bradycardia, hypotension) on a monthly basis for the duration of the study. These safety endpoints are collected at each study visit and recorded in the study database. Patients are routinely assessed for these side effects in the PACU by their bedside nurse as well as the anesthesia resident who is responsible for discharging them from the PACU.

| | | Subgroup n=6 | | Total N=36 | |
|-------------|---|--------------|---------------------|------------|---------------------|
| Event | Assumed Probability Risk (upper end) | p<0.01 | Safety cut short if | p<0.01 | Safety cut short if |
| Nausea | | | | | |
| (high) | 0.25 | p=0.0046 | n≥5 | p=0.0086 | n≥16 |
| Vomiting | | | | | |
| (high) | 0.15 | p=0.0059 | n≥4 | p=0.0048 | n≥12 |
| Bradycardia | | | | | |
| (high) | 0.05 | p=0.0022 | n≥3 | p=0.0083 | n≥6 |
| Hypotension | | | | | |
| (high) | 0.15 | p=0.0059 | n≥4 | p=0.0048 | n≥12 |

Using the binomial equation (see below), we calculated the probability of seeing a set number of patients in each group, if the actual probability in the normal surgical population is at the level specified in the 'assumed probability' column.

For example, if the 'normal' probability of nausea is up to 25% (that is, the risk with treatment is the same as the risk under standard surgical conditions), then the chance of having 5 or more patients with nausea in any one treatment group is 0.0046, and the chance of having 16 or more patients with nausea in total is p=0.0048. Since this is unlikely, we will reject the null hypothesis, and conclude that the actual risk in our trial is actually higher than that. So if 5 or more patients report nausea in any one group or if 16 or more patients report nausea in total, this would trigger a suspension of the trial for further review.

Page 15 of 30 Version: 3 (10/14/2024)

$$P(X \ge x) = \sum_{x}^{N} {N \choose x} p^{x} (1-p)^{(N-x)}$$

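### Tachycardia is a Section 4 safety outcome but is left out of Section 21's named monthly endpoints and its threshold table, so no prespecified suspension trigger applies to it

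*Combined protocol and SAP*

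**What the plan says.** **Outcome.** Section 4 (Study Endpoints) lists five safety outcomes measured in the PACU: nausea, vomiting, bradycardia, tachycardia and hypotension. A footnote defines tachycardia as "Heart rate > 100 beats per minute over two or more recordings if not present pre-operatively".

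**Risk.** Section 17 places tachycardia (2-5%) and bradycardia (1-5%) in the list headed "Uncommon but serious risks of sugammadex include".

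**Data.** Section 20 collects all five events on one line of the form.

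**Monitoring.** Section 21 states: "The study team will review the safety endpoints (nausea, vomiting, bradycardia, hypotension) on a monthly basis". The table below that sentence has rows for these four events only. Each row gives an assumed probability, a count out of 6 for any one dose group and a count out of 36 overall, chosen so that the binomial tail is below 0.01. The worked example for nausea says that reaching either count suspends the trial for review.

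**General review.** Section 21 also collects any other adverse events up to PACU discharge. Monitoring Table 3 has the PI review data as they are collected and, every month, review all adverse events and monitor critical data points, including study endpoints. No count or action is attached to these reviews.

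**The concern.** Section 21 speaks of the safety endpoints as a set, then gives four of the five that Section 4 defines, without a reason. The sentence and the table omit the same event.

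Rarity or lack of seriousness does not explain it. Bradycardia and tachycardia stand in the same risk list with the same upper end, tachycardia has the higher lower end, and bradycardia has a row.

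At stake is consistency in a safety rule for a dose-response study that the protocol classes as more than minimal risk. Three bradycardia cases among the six patients at one dose meet a written suspension criterion. Three tachycardia cases at that dose, or six, meet none. The per-group column exists to pick up a signal confined to one dose, and for this outcome it is absent.

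**Working it through.** **Inputs.** From Section 21: group size 6, total 36, tail limit 0.01, and assumed probabilities of 0.25 (nausea), 0.15 (vomiting), 0.05 (bradycardia) and 0.15 (hypotension). From Section 17: tachycardia 2-5%. From Table 1 in Section 7: six dose groups of 6, placebo included.

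**Step 1: reproduce the plan's table.** The formula is P(X ≥ r) = Σ C(n,k) p^k (1−p)^(n−k), summed from k = r to n. The threshold is the smallest r with a tail below 0.01.

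| Event | p | r of 6 | Tail | Tail at r−1 | r of 36 | Tail | Tail at r−1 |
|---|---|---|---|---|---|---|---|
| Nausea | 0.25 | 5 | 0.0046 | 0.0376 | 16 | 0.0086 | 0.0209 |
| Vomiting | 0.15 | 4 | 0.0059 | 0.0473 | 12 | 0.0048 | 0.0137 |
| Bradycardia | 0.05 | 3 | 0.0022 | 0.0328 | 6 | 0.0083 | 0.0324 |
| Hypotension | 0.15 | 4 | 0.0059 | 0.0473 | 12 | 0.0048 | 0.0137 |

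All eight tabulated probabilities agree to four decimals, and every threshold is the smallest that qualifies. (The worked example in the text gives 0.0048 for 16 or more nausea events in total; the table's 0.0086 is the correct value. That slip does not affect this point.)

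**Step 2: the missing row.** At p = 0.05 and n = 6:

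P(X ≥ 3) = 20(0.05)³(0.95)³ + 15(0.05)⁴(0.95)² + 6(0.05)⁵(0.95) + (0.05)⁶ = 0.00214 + 0.00008 + 0.000002 + 0.00000002 = 0.0022.

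Two or more gives 0.0328, so the threshold is 3 of 6. For n = 36, P(X ≥ 6) = 0.0083 and P(X ≥ 5) = 0.0324, so the threshold is 6 of 36. This equals the bradycardia row. At the lower end of 2%, the same method gives 2 of 6 (0.0057) or 4 of 36 (0.0057).

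**Step 3: false suspension.** For one event, the chance of no trip is the probability that all six groups stay below the group threshold and the total stays below the overall threshold. It is found by convolving six binomial(6, p) distributions, each cut off at r−1, and summing over totals below the overall threshold. The chance of a trip by row is then:

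- nausea: 0.0332
- vomiting: 0.0372
- bradycardia: 0.0191
- hypotension: 0.0372

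Taking events as independent and each at its assumed rate:

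- Four rows: 1 − (0.9668)(0.9628)(0.9809)(0.9628) = 0.121.
- With a tachycardia row at 5%: 1 − (1 − 0.1208)(0.9809) = 0.138.

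The increase is 13.8 − 12.1 = 1.7 percentage points.

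**Step 4: sensitivity to the true rate.** With the tachycardia thresholds fixed at 3 of 6 and 6 of 36, the new row alone trips with these probabilities:

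| True rate in every group | Row trips |
|---|---|
| 5% | 1.9% |
| 10% (assumed) | 18% |
| 15% (assumed) | 50% |
| 20% (assumed) | 78% |

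The rates above 5% are illustrations; the documents give none for the trial's own definition.

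**The case against.** The strongest objection concerns the consequence. A reader might infer that tachycardia goes unreviewed, that an excess could not prompt a review, or that no number of events could suspend the trial. The documents do not support this. Monitoring Table 3 gives the PI a real-time review of data, a monthly review of all adverse events and monthly monitoring of study endpoints, and tachycardia falls under all three. Nothing says that the four rows are the only grounds for suspension. This part of the objection stands: what is missing is a prespecified numerical trigger, not oversight. It does not remove the inconsistency, because the same general reviews cover the four listed events and the plan still set thresholds for those.

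A second objection is that choosing which events get a threshold is a design decision: pain and anaphylaxis are also listed risks without rows. That is fair, but neither is a Section 4 safety outcome. Tachycardia is the only one of the five left out.

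A third is that 5% may be the wrong reference. Section 21 describes its assumed probabilities as those of the normal surgical population, whereas the 2-5% in Section 17 is given as a risk of sugammadex, and nothing shows that it used the trial's heart-rate definition. If the background rate is higher, the row trips by chance more often. This stands as a limit on the cost estimate. It applies equally to the existing bradycardia row, so it does not justify the omission.

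**Conclusion.** The point holds as an internal inconsistency between Section 21 and Section 4. Tachycardia, a named and collected safety outcome with the same 5% upper end as bradycardia, has no prespecified suspension threshold and is not among the endpoints named for the study team's monthly review. Only the PI's general review, exercised by judgement, would catch an excess.

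The gap is modest because that review exists, but it lies in a safety rule and is cheap to close. The thresholds in Step 2 rest on taking 5% as the reference rate. The 1.7-point increase rests further on independence between events and on every event occurring at exactly its assumed rate, so it should not be quoted without the range in Step 4.

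**What to change.** Reconcile Section 21 with Section 4: add tachycardia to the monthly review sentence and add a table row calculated by the plan's own method. At the Section 17 upper end of 5%, the row reads n≥3 of 6 (p=0.0022) and n≥6 of 36 (p=0.0083). State the basis for the assumed rate under the trial's definition of tachycardia and, if a different rate is adopted, recompute the row before use. If the omission was deliberate, Section 21 should give the reason and say that tachycardia is covered by the PI's general review alone.

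The cost is one table row and one word in a sentence. The data are already collected and no patient procedure changes. The statistical price is the added chance of a false suspension: small if the background rate is near 5%, substantial if it is 10% or more.
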